
 To evaluate the efficacy of lasmiditan 200 mg, 50 mg, and 100 mg on Patient Global Impression of Change (PGI-C) compared to placebo 	
 The proportion of patients in each group very much or much better as measured by PGI-C, at 2 and 24 hours postdose during the attack

 To evaluate the efficacy of lasmiditan 200 mg, 100 mg, and 50 mg on Health-Related Quality of Life (HRQoL) during an acute migraine attack compared to placebo 	
 Mean HRQoL score for domains of social functioning, migraine symptoms, and feelings/concerns, as measured by the 24-hour Migraine Quality of Life Questionnaire (MQoLQ), in each group at 24 hours postdose

Abbreviations: 24-hour MQoLQ = 24-Hour Migraine Quality of Life Questionnaire; EQ-5D-5L = EuroQol 5-dimension 5-level scale; HRQoL = Health-Related Quality of Life; MBS = the most bothersome symptom as identified by the individual from the associated symptoms of nausea, phonophobia or photophobia; PGI-C = Patient Global Impression of Change; HRQoL = Health-Related Quality of Life.

Summary of Study Design:

Study LAIH is a prospective, multicenter, randomized, double-blind, placebo-controlled Phase 2 study of Japanese adult patients suffering from migraine with or without aura.

Summary of Treatment Arms and Duration:

Each patient's study participation will consist of a screening visit (Visit 1) followed by a randomization visit (Visit 2) 7 to 30 days after screening, a treatment period of up to 8 weeks and an end of study (EoS) visit (Visit 3) 3 to 28 days after treating the migraine attack (or at 8 weeks [+2 weeks as visit allowance] after Visit 2).

Patients will be asked to treat a migraine attack with study drug on an outpatient basis. Patients will be provided with doses for treatment of the attack at Visit 2; placebo, lasmiditan 50 mg, 100 mg, or 200 mg will be assigned. [Table LAIH.1](#) shows the treatment group assignments for Study LAIH.

To achieve between-group comparability, the randomization will be stratified (yes or no) for current use of concomitant medication(s) that reduce the frequency of migraine episodes.

Table LAIH.1. Treatment Groups

Treatment Groups	Treatment Dose
1	Placebo
2	Lasmiditan 50 mg
3	Lasmiditan 100 mg
4	Lasmiditan 200 mg

Summary of Number of Patients:

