		+7~30 days after V1	8 weeks	3~28 days after treatment OR At 8 weeks after V2 ^d	
Obtain informed consent	X				
Inclusion and exclusion criteria	X				
Demographics	X				Demographics will include age and sex.
Physical examination	X			X	
Diagnosis of migraine	X				Document migraine characteristics per IHS (ICHD-2) criteria.
Vital signs	X			X	Vital signs will include temperature, blood pressure, and pulse. Blood pressure and pulse will be measured in the sitting position prior to blood draws and dosing. Blood pressure: use local site blood pressure equipment.
Weight	X			X	
Height	X				
Employment status		X			
Complete MIDAS	X				
Complete mTOQ-6		X			
Review migraine history including prior treatment	X				Timing of onset, frequency of migraine headache, existence of aura, and prior therapy for migraine will be collected.
Review medical history and concomitant medications	X				Medical history (including risk factors for CVD and family history of CVD) will be collected.
Adverse events		X		X	
Concomitant medications		X		X	
Menstrual cycle status		X		X	Female patients will be asked the beginning date and the end date of their menstrual period at V2 and V3.

Procedure	Visit 1 ^a Screening	Visit 2 Baseline	Treatment period ^b Treat moderate/severe migraine attack within 4 hrs of pain onset	Visit 3 EoS or EDC ^c	Note
		+7~30 days after V1	8 weeks	3~28 days after treatment OR At 8 weeks after V2 ^d	
Neurological examination	X			X	
12-lead ECG	X			X	The ECG should be collected prior to blood draws. Patients must be supine for approximately 5 to 10 minutes before ECG collection and remain supine but awake during ECG collection.
Clinical laboratory (hematology, serum chemistry, urinalysis) ^e	X			X	The hepatic algorithm will be triggered in cases of hepatic abnormalities identified by laboratory testing.
Serum pregnancy test or FSH	X			X	Pregnancy tests assessed in WOCBP; FSH assessed as appropriate only at V1 (details in Inclusion Criteria [8] in Section 6.2)
Alcohol abuse/dependence and smoking status	X				
Urine drug screen	X				Can be repeated once if the result is positive.
Pharmacogenetic sample (genetic sample/DNA)	X				
C-SSRS - baseline/screening version/ SHSF, SHFU	X				A SHFU form will be completed where applicable.
C-SSRS - since last visit version/SHSF, SHFU		X		X	A SHFU form will be completed where applicable.
Confirm eligibility		X			
Patient training video		X			
Randomization		X			
Dispense study drug		X			

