5.1. Overall Design

Study LAIH is a prospective, multicenter, randomized, double-blind, placebo-controlled Phase 2 study of Japanese adult patients suffering from migraine with or without aura. Patients will have a history of migraine for at least 1 year, 3 to 8 migraine attacks per month, and disabling migraine as defined by a Migraine Disability Assessment Test (MIDAS) score ≥ 11 . Patients will be asked to treat a single migraine attack with study drug on an outpatient basis. At Visit 2, patients will be provided with doses for treatment of an attack; placebo, lasmiditan 50 mg, 100 mg, or 200 mg will be assigned.

[Table LAIH.1](#) shows the treatment group assignments for this study.

Each patient's study participation will consist of a screening visit (Visit 1), followed by a randomization visit (Visit 2) 7 to 30 days after screening, a treatment period of up to 8 weeks, and an EoS visit (Visit 3) 3 to 28 days after treating the migraine attack (or at 8 weeks [+2 weeks as visit allowance] after Visit 2). If a migraine attack is treated, the EoS visit must occur no later than 28 days following treatment of the migraine attack. Sites will encourage patients to visit as early as possible following treatment of the migraine attack.

[Figure LAIH.1](#) illustrates the study design.

Abbreviations: EDC = early discontinuation; EoS = end of study.

- a Preventive treatment allowed (if stable 3 months prior to Visit 1).
- b Patients will take 3 tablets to maintain blinding.
- c Patients will wait to take study drug until migraine pain is moderate/severe; must be the FIRST treatment for the migraine taken within 4 hours of pain onset.
- d Patients who do not treat a migraine with study drug should attend Visit 3 at 8 weeks after Visit 2. Visit 3 should be finished by 8 weeks (+14 days as visit allowance) after Visit 2.

Figure LAIH.1. Patient flow overview Clinical Protocol H8H-JE-LAIH.

Study governance considerations are described in detail in [Appendix 3](#).

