5.1.2. Randomization (Visit 2)

At Visit 2, patients will be randomly assigned treatment as described in Section 7.1, will have additional assessments (see Section 2), will be dispensed study drug, and will begin the Treatment Period. If available and where the Institutional Review Board (IRB) allows, patients will also watch a training video designed to address patient expectations with regard to participation in a placebo-controlled trial and the difference between medical treatment and research. The patient will receive detailed instructions on the use of the eDiary and on dosing their migraine attack with study drug.

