8.1. Discontinuation from Study Treatment

This is a single-dose study. If a patient discontinues prior to receiving the single dose of lasmiditan within 8 weeks of treatment period, early termination procedures will be completed per Section 2 (Schedule of Activities), Section 9.2 (Adverse Events), and Section 9.4 (Safety) of this protocol.

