- Post-dose AEs
 - By PT by decreasing frequency
 - By SOC/PT (sorted alphabetically by system organ class (SOC), then by frequency in preferred term (PT))
- TEAEs by PT considered to be related to investigational product by investigator
- TESAEs by PT
- TESAEs by PT considered to be related to investigational product by investigator
- SAEs by PT

Listing of AE (with TEAE flag) will be created for all randomized population

List of SAE will be created.

Note: If multiple severities are reported for a given AE and subject, then the most severe intensity will be counted. The same rule is applied for TEAEs.

Note: Patients were told not to report symptoms that usually occurred during migraine attacks (e.g. nausea).

Note: For events that are gender-specific, the denominator and computation of the percentage will include only patients from the specific gender.

5.7.2. *Columbia-Suicide Severity Rating Scale (C-SSRS)*

The C-SSRS will be used to assess suicidal ideation, suicidal behavior, and self-injurious behavior without suicidal intent. At Visit 1, the screening version will be used to assess suicidal ideation and behavior during the lifetime and in the past one month. At the following visits (Visit 2, EOS/Visit 3), the Since Last Visit version will be used to assess suicidal ideation and behavior since the last visit.

The following outcomes are C-SSRS categories and have binary responses (yes/no).

Category 1 – Wish to be Dead

Category 2 – Non-specific Active Suicidal Thoughts

Category 3 – Active Suicidal Ideation with Any Methods (Not Plan) without Intent to Act

Category 4 – Active Suicidal Ideation with Some Intent to Act, without Specific Plan

Category 5 – Active Suicidal Ideation with Specific Plan and Intent

Category 6 – Preparatory Acts or Behavior

Category 7 – Aborted Attempt

Category 8 – Interrupted Attempt

Category 9 – Actual Attempt (non-fatal)

Category 10 – Completed Suicide

Self-injurious behavior without suicidal intent is also a C-SSRS outcome (although not suicide-related) and has a binary response (yes/no).

Composite endpoints based on the above categories are defined below.

- Suicidal ideation: A “yes” answer at any time during treatment to any one of the five suicidal ideation questions (Categories 1-5) on the C-SSRS.
- Suicidal behavior: A “yes” answer at any time during treatment to any one of the five suicidal behavior questions (Categories 6-10) on the C-SSRS.

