- Suicidal ideation or behavior: A “yes” answer at any time during treatment to any one of the ten suicidal ideation and behavior questions (Categories 1-10) on the C-SSRS.

Summary of 10 categories and “Self-injurious behavior without suicidal intent” will be created for baseline (Visit 1 and Visit 2 separately) for safety population and for all randomized population.

Summary of 10 categories and “Self-injurious behavior without suicidal intent”, and 3 composite endpoints will be summarized will be created for post baseline for safety population and for all randomized population.

Listings will present all C-SSRS data for subjects with at least one positive response to any C-SSRS question at any time during the study for all randomized population

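### The Visit 3 C-SSRS recalls everything since Visit 2, and SAP 5.7.2 tabulates it as post-baseline by drug used without separating answers that arose before the single dose

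*Protocol*

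**What the plan says.** Protocol Section 2 (Table LAIH.2) schedules the screening C-SSRS at Visit 1 and the "C-SSRS - since last visit version/SHSF, SHFU" at Visits 2 and 3. None is scheduled at or near dosing. At Visit 2 patients "will be dispensed study drug, and will begin the Treatment Period" (Protocol 5.1.2). That period is "a treatment period of up to 8 weeks" (Protocol 5.1). Protocol 8.1 states "This is a single-dose study", and the synopsis places "an end of study (EoS) visit (Visit 3) 3 to 28 days after treating the migraine attack".

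SAP 5.7.2 confirms the recall window: after Visit 1, "the Since Last Visit version will be used to assess suicidal ideation and behavior since the last visit". It treats Visits 1 and 2 as baseline. The ideation composite is a yes "answer at any time during treatment to any one of the five suicidal ideation questions", and the other two composites use the same time wording. Of the post-baseline summary it says "3 composite endpoints will be summarized will be created for post baseline for safety population", and it adds the all-randomized population. SAP 5.3 analyses the safety population by the drug actually used. Nothing in SAP 5.7.2 compares an answer with the time of the dose.

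**The concern.** A safety-population table by drug used is read as what happened after exposure. Here one yes/no answer merges two periods: the undosed wait from Visit 2 to the dose, and the time from the dose to Visit 3. Ideation during the wait would be counted against a drug the patient had not yet taken, and a real effect of the dose would be diluted by untreated time.

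The SAP treats other safety data differently. SAP 5.7.1 ties both treatment-emergent and post-dose adverse events to the dose. For vital signs and laboratory tests, SAP Section 3 says the treatment-emergent label was dropped because Visit 3 generally falls more than 48 hours after dosing. The C-SSRS received neither a dose anchor nor a label that makes its window clear.

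Positive answers are likely to be few, so each one is visible. At the planned numbers, a single yes is 1/81 = 1.2% of the 50 mg arm and 1/190 = 0.5% of placebo.

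**Working it through.** The plan states no figure on this point, so there is none to reproduce. The check is day arithmetic on the recall window.

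**Inputs**
- Wait from Visit 2 to the dose, d: 0 to 56 days (Protocol 5.1).
- Dose to Visit 3, f: 3 to 28 days (Protocol 5.1).
- Visit 3 finished by 56 + 14 = 70 days after Visit 2 (Table LAIH.2, footnote d). I take this limit to cover dosed patients too.
- Attack frequency: 3 to 8 per month (Protocol 6.2).
- Not dosing within 8 weeks: about 29% (Protocol 10.1.1).

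**Formula.** Pre-dose share of the Visit 3 window = d/(d + f).

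**Two illustrations of the wait, both assumptions**
1. The first attack is treated, attacks are evenly spaced and a month has 30 days. The wait is then 30/8 = 3.75 days to 30/3 = 10 days.
2. The daily chance of dosing is constant and fitted to the 29%. The rate is -ln(0.29)/56 = 0.0221 per day. The mean wait among those who dose is 1/0.0221 - 56 × 0.29/0.71 = 22.4 days.

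**Pre-dose share**

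| d (days) | f = 3 | f = 14 | f = 28 |
|---|---|---|---|
| 0 | 0% | 0% | 0% |
| 3.75 | 56% | 21% | 12% |
| 10 | 77% | 42% | 26% |
| 22.4 | 88% | 62% | 44% |
| 28 | 90% | 67% | 50% |
| 56 | 95% | 80% | past day 70 |

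For example, 3.75/31.75 = 12%, 10/13 = 77%, 22.4/25.4 = 88% and 56/59 = 95%. The 22.4-day row is the share at the mean wait, not the mean of individual shares. Protocol 5.1 has sites encourage an early Visit 3, which moves patients towards the left-hand columns.

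**Dilution.** Suppose events otherwise occur at a constant rate and the dose doubles that rate for 48 hours. The ratio seen over a window of W days is (W + 2)/W = 1 + 2/W.
- Dose to Visit 3 only (W = f): 1 + 2/3 = 1.67 at f = 3, and 1 + 2/28 = 1.07 at f = 28.
- Planned window, d = 3.75 to 10: 1.30 to 1.15 at f = 3, and 1.06 to 1.05 at f = 28.
- Planned window, d = 22.4: 1.08 at f = 3, and 1.04 at f = 28.

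The loss is substantial when Visit 3 is early and slight when it is late.

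**Do other parts of the plan separate the two periods?**
- Protocol 9.4.4: a non-serious event first found by the C-SSRS, and not leading to discontinuation, stays off the AE form. For such events AE dating gives no help.
- SAP 5.7.7.4: the suicide/self-injury table covers all AEs after Visit 1 through Visit 3, so it is not split at the dose.
- SHSF and SHFU forms: they are scheduled with the C-SSRS and may hold dates, but the documents do not describe their content and the SAP does not use them for this.
- SAP 5.7.2 listing: it shows all C-SSRS data for anyone with a positive answer, with no timing relative to the dose specified.

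**The case against.** The strongest reply is that the labels are right on the protocol's own terms. The Treatment Period begins at Visit 2, and Visits 1 and 2 are the C-SSRS baseline, so a Visit 3 yes is post-baseline and falls during treatment. That stands. A reader might infer that the table breaks the protocol's definitions, and the documents do not support this. The mismatch is with drug exposure, which a table by drug used invites the reader to assume.

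A reader might also infer a biased comparison or a missed serious signal. Neither follows. Assignment is randomized and double-blind, so pre-dose events should fall across arms in proportion to arm size. Safety is descriptive with no tests (SAP 5.4). An event that is serious or leads to discontinuation goes on the AE form even when the C-SSRS finds it first (Protocol 9.4.4), with a time of onset (Protocol 9.2). Exclusion [17] also removes patients with recent serious ideation or behaviour.

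Nor do the documents show that sites cannot date a positive answer. The SAP describes the analysis variable as yes/no, and the SHSF or SHFU may contain dates. What remains is that the plan does not use any such dates.

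Finally, the 22-day wait should not be taken as established. The constant-rate model treats every non-doser as still waiting and implies an untruncated mean wait of 1/0.0221 = 45 days, which is long for patients with 3 to 8 attacks a month. This is a fair criticism, and it is why the shorter waits are shown beside it.

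**Conclusion.** The point holds as a gap in attribution. In dosed patients the Visit 3 C-SSRS cannot, as planned, distinguish events before the dose from events after it, and SAP 5.7.2 reports both as post-baseline by drug used. The consequence is non-directional dilution and misattribution in a descriptive safety table, mainly for non-serious events that only the C-SSRS elicits.

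Its size depends on a wait the documents do not give. The pre-dose share is zero for a dose on the day of Visit 2, and the ranges above it rest on the stated assumptions about attack spacing or dosing rate. It exceeds half in many plausible cases with an early Visit 3, and is 12-26% for waits of about 4 to 10 days with Visit 3 at day 28. The change is worth making because it is cheap, not because any trial conclusion depends on it.

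**What to change.** - **CRF.** For each positive Visit 3 C-SSRS item in a dosed patient, record whether it first occurred before or after study drug intake, with a date. If the SHSF or SHFU already holds that date, use it and add nothing.
- **SAP 5.7.2.** In the safety population, define the post-baseline categories and the three composites as occurrence at or after dosing. Show positives between Visit 2 and the dose separately as pre-dose.
- **Listing.** Add the dose date and the before/after timing to the planned C-SSRS listing.

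The cost is one field completed only for positive answers, plus SAP wording. No visit, assessor or sample size changes. The drawback is that timing relies on patient recall, sometimes weeks later, so some answers will be uncertain. If the CRF can no longer be changed, the SAP can at least state that the C-SSRS window starts at Visit 2 and show the dose date in the listing.

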3.1. Study Rationale

In 2 Phase 3, randomized, double-blind, single migraine attack studies (Study COL MIG-301/H8H-CD-LAHJ [Study 301/LAHJ, SAMURAI] and Study COL MIG-302/H8H-CD-LAHK [Study 302/LAHK, SPARTAN]), lasmiditan (Study 301/LAHJ: 100 mg and 200 mg, Study 302/LAHK: 50 mg, 100 mg, and 200 mg) demonstrated statistically significant superiority versus placebo in the proportion of patients who were headache pain free at 2 hours postdose as well as the proportion of patients who were free of their migraine-associated MBS (as identified by the patient from the associated symptoms of nausea, phonophobia or photophobia) at 2 hours postdose.

Lasmiditan in Japan is currently being developed for patients with migraine based on the bridging strategy described in the Guidance on Ethnic Factors in the Acceptability of Foreign Clinical Data (ICH-E5). Influences of ethnic factors on lasmiditan were evaluated in the Phase 1 Study H8H-JE-LAIE (Study LAIE), in which a randomized, 3-period, subject- and investigator-blind, crossover design was implemented to explore the safety, tolerability, and PK of lasmiditan in healthy Japanese and Caucasian subjects. The study had 3 cohorts, 2 of which included only Japanese subjects (Cohorts 1 and 2) and 1 (Cohort 3) which included only Caucasian subjects. Subjects were enrolled into 1 of 3 cohorts. Within each cohort, subjects were randomized to a specific treatment sequence. Randomization was stratified by sex to ensure approximately an equal number of male and female subjects in each cohort and treatment sequence. Subjects received single oral doses of 400 mg, 2 × 200 mg (repeated single doses, 2 hours apart), 200 mg, 100 mg, 50 mg lasmiditan, placebo, or 2 × placebo (repeated single doses, 2 hours apart) (Japanese subjects, Cohorts 1 and 2), or 200 mg, 100 mg, 50 mg, or placebo (Caucasian subjects, Cohort 3) on Day 1 of each period, according to their assigned treatment sequence. There was a washout period of approximately 72 hours between dose administrations across periods.

Overall, a total of 27 healthy subjects, consisting of 16 Japanese subjects (8 male and 8 female), and 11 Caucasian subjects (6 male and 5 female), between the ages of 29 and 63 years, and 24 and 64 years, respectively, participated in Study LAIE. Of the 27 subjects who entered the study, 27 were randomly assigned to treatment and received at least 1 dose of study drug. Twenty six subjects completed the study, and 1 did not complete the study (withdrew due to a family emergency).

Safety data in Japanese and Caucasian subjects from Study LAIE showed that no deaths, or serious or severe adverse events (AEs) occurred during the study. There were no discontinuations due to AEs. The most frequent treatment-emergent adverse events (TEAEs) (all causalities) reported during the study were somnolence, dizziness, and hypoesthesia in decreasing order in the overall population of Japanese and Caucasian subjects combined. In the Integrated Safety Summary (ISS), a summary of TEAEs in non-Japanese healthy subjects (556 healthy subjects, non-elderly, 79% White) who were administered with single doses of lasmiditan over a range of 0.1 mg to 400 mg, the most frequent TEAEs reported were dizziness, somnolence, fatigue, headache, paraesthesia, and nausea in decreasing order. The TEAEs and

their frequency reported in Japanese subjects in Study LAIE are generally similar to those in the ISS. Taken together, these data suggest that there are no major differences in safety and tolerability in Japanese and non-Japanese healthy subjects. The frequency of TEAEs in Study LAIE did not differ between sexes in Japanese subjects, whereas a higher frequency of TEAEs were observed in Caucasian females. No clinically significant effect of lasmiditan on systolic blood pressure, diastolic blood pressure, or QTc interval was observed during Study LAIE across the doses investigated.

The PK data from Study LAIE appeared to be similar in Japanese and Caucasian subjects with median maximum concentration between 1.50 and 2.50 hours, and mean $t_{1/2}$ value approximately 4 hours for all dose levels and across populations. No consistent difference in the PK of lasmiditan and its metabolites was noted between male and female subjects within Japanese and Caucasian populations.

Overall, the safety and PK results in Japanese and Caucasian healthy subjects in Study LAIE and the ISS, indicate that lasmiditan is unlikely to be affected by intrinsic ethnic factors, thus supporting the conclusion that the bridging strategy can be employed for the development of lasmiditan in Japan.

The current study (H8H-JE-LAIH [LAIH]) will be conducted as the bridging trial to the Phase 3 Study 302/LAHK with dose response in efficacy in the range of 50-200 mg. Study LAIH will assess the efficacy and safety of lasmiditan in acute treatment of a single migraine attack in Japanese adult patients with or without aura.

